4.1 Treatment Assignment

Eligible patients will be assigned a randomization number in sequential order and each of the randomization will determine the allocation of one of the two groups in 1:1 ratio as shown below:

Treatment Group:

TWB-103 add-on TegadermTM till 100% re-epithelialization or up to 10 days, whichever comes first, followed by TegadermTM alone application from Day 10 to Day 14 if failing to achieve 100% re-epithelialization by Day 10. If 100% re-epithelialization is not observed on Day 14 (the end of treatment), patients will have application of TegadermTM up to Day 28.

Control Group:

Placebo+TegadermTM till 100% re-epithelialization or up to 10 days, whichever comes first, followed by TegadermTM alone application from Day 10 to Day 14 if failing to achieve 100% re-epithelialization by Day 10. If 100% re-epithelialization is not observed on Day 14 (the end of treatment), patients will have application of TegadermTM up to Day 28.

Note:

1. TegadermTM will be renewed at each visit between Visit 3 (Day 3) to Visit 7 (Day 28) if 100% re-epithelialization is not observed. Whenever TegadermTM falls off from DSW site, new TegadermTM should be applied immediately. If necessary, drainage is allowed, but re-application of TWB-103 or placebo is not necessary in this case.
2. If the first 100% re-epithelialization is observed on Day 28, patients will be scheduled Day 42 follow-up and dispensed with TegadermTM.

3. If the first 100% re-epithelialization is not observed on Day 28, patients will receive the application of Tegaderm™ on site for protection of wound site and/or have other appropriate treatment at the investigator's discretion. The DSWs will be followed till 100% re-epithelialization.

4. To prevent the itchiness and skin reaction caused by the long-term usage of Tegaderm™, Vaseline Gauze or Non-Stick Gauze such as silastic foam dressings can be used on and after Day 14 at the investigator's discretion.

4.2 Randomization and Blinding

Permuted block randomization method stratified by site will be applied to generate randomization codes, detailed in the randomization plan. Each randomization number will be assigned to individual patients according to the time-sequence for screened patient becoming eligible.

Blinding to patients and the investigator will be performed in this study. Besides, the evaluator blinding on wound healing evaluation will also be performed that an additional evaluator who is not aware of the treatment given will assess based on the photos of the wound. A second additional evaluator, who is also blinded, will be requested when the discrepancy occurs between the investigator and the first additional evaluator in the determination of 100% re-epithelialization.

At the initiation of the study, the study center will be instructed on the method for breaking the blind. The emergency key (individual random code envelope) will be kept by the investigator. Study drug treatment may be revealed only for reasons relating to the subject's safety and when critical therapeutic decisions are contingent on knowing the assigned study drug, including conditions listed in Section 4.3.1 and 4.3.2. Withdrawal of a subject from the study is not a sufficient reason to break the blind.

The reason to break the blind must be discussed with the Sponsor prior to breaking the blind. Investigator can request this by using the “Emergency Key Open Request Form” and sending it to the sponsor’s representative with the rationale described. After receiving authorization for unblinding from the Sponsor, the investigator will acknowledge with his/her signature and the date on the Emergency Key envelope, then open to unblind the specific subject’s treatment assignment. When the blinding code is broken, the reason must be fully documented as a written entry in the source document.

Key information will be recorded in the “Emergency Key Open Request Form”, including the subject number, the date the blind was broken, the rationale, the person who requested the breaking of the blind, and the signatures of the Sponsor representative contacted, and the person who broke the blind. The incidence of blind broken should be documented in the subject’s case report form (CRF), but no emergency key should be revealed.

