4.3 Stopping rules and unscheduled visits

4.3.1 Stop the study

The study will be stopped when > 1/3 of patients in the phase I have developed study drug related grade 2 or above SAEs defined as in Section 8. The investigator will determine if SAEs are study drug related without breaking the blind. If the cause of SAE is inconclusive, the investigator can request to break the blind following the procedure stated in Section 4.2.

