4.3.2 Discontinue the study product

Patients who experience > Grade 2 skin allergic reaction or > Grade 2 systemic allergic reaction related to the product or placebo must not receive any further TWB-

103 or placebo treatment. If a patient should develop infection at DSW site before Day 10, he/she will stop the TWB-103 or placebo application at the investigator's discretion. Patients with the aforementioned conditions, before or at Visit 8, should finish the scheduled assessments (except that application of TWB-103/placebo is stopped; that the application and dispensation of Tegaderm™ will be at the investigator's discretion; and that the return of Tegaderm™ will be asked if applicable). Patients with allergic reaction or infection may receive appropriate treatments at the PI's discretion, will be monitored throughout the healing process (including the recovery from allergic reaction or infection, and the complete closure of DSW) and will continue the remaining visits (application of TWB-103 or placebo will be stopped if planned originally). In these cases of TWB-103/placebo discontinuation, wound assessments performed after onset of allergic reaction or infection will be excluded from statistical analysis.

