11.2 IRB review

This protocol and the associated informed consent documents must be submitted to the IRB for review and approval. The study will not be initiated until the IRB provides written approval of the aforementioned documents and until approval documents have been obtained by the Principal Investigator and CRO.

No changes from the final approved protocol will be initiated without the IRB/IEC's prior written approval or favorable opinion of a written amendment, except when

necessary to eliminate immediate hazards to the study participants or when the change involves only logistics or administration. Any significant deviation from the protocol when no approved amendment exists will be regarded as a protocol violation, and will be addressed as such during the reporting of the study.

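### Section 4.2 makes every opening of the emergency code wait for sponsor authorisation, with no stated emergency exception or response time

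*Combined protocol and SAP*

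**What the plan says.** Section 4.2 (Randomization and Blinding) first deals with access: "The emergency key (individual random code envelope) will be kept by the investigator". It then limits use to reasons of subject safety and to situations "when critical therapeutic decisions are contingent on knowing the assigned study drug", and it names the conditions of Sections 4.3.1 and 4.3.2 as included.

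The next paragraph sets the procedure: "The reason to break the blind must be discussed with the Sponsor prior to breaking the blind". A request form with the rationale goes to the sponsor's representative. The opening step follows: "After receiving authorization for unblinding from the Sponsor, the investigator will acknowledge with his/her signature and the date on the Emergency Key envelope", and only then is the envelope opened. The form also records the signature of the sponsor representative who was contacted. The reason is written in the source document, and the fact of unblinding is noted in the CRF.

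Section 4.3.1 and the Protocol Summary send an SAE of inconclusive cause down the same path: "the investigator can request to break the blind following the procedure stated in Section 4.2".

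**The concern.** An envelope held at the site normally exists so that a clinician facing an emergency can learn the assignment without waiting for anyone else. Here every opening that complies with the protocol waits for a third party's consent, and the plan does not say how soon that consent must come. An investigator with a patient whose treatment depends on the code would have to wait or depart from Section 4.2.

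The setting gives the question some weight. This is the first use of TWB-103 in humans (Sections 1.2.1 and 1.2.4), and the product contains living allogeneic cells. The control is freezing solution in the same gelatin hydrogel, so the code tells the clinician whether the patient was exposed to the cells. Section 10.2.4 states that there is no DSMB, and the plan names no other party who could authorise an opening. What is at stake is participant safety and trial conduct, not an analysis result.

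**Working it through.** No arithmetic applies to the main point. The check is whether any text relaxes the authorisation step, and then how often that step could matter.

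**1. Purpose against procedure (Section 4.2).**
- When the code may be revealed: subject safety, and critical treatment decisions that depend on the assignment.
- Who holds it: the investigator.
- How it is opened: discussion with the sponsor, request form, sponsor authorisation, signature and date, opening.
- Requests exempt from the authorisation step: none stated.

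**2. Search for an exception elsewhere.**
- Protocol Summary and Section 4.3.1: refer back to Section 4.2 and add no separate route.
- Section 4.3.2: covers stopping the product and treating reactions; silent on unblinding.
- Section 8.3.2: the 24-hour limit is for the investigator's SAE report to the sponsor or CRO, not for the sponsor's reply to an unblinding request.
- Section 11.2: the clause on changes "necessary to eliminate immediate hazards to the study participants" concerns protocol changes made before IRB approval. It does not mention unblinding or waive sponsor authorisation.

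No exception is found.

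**3. Time limits.** Section 8.3.2 sets several: 24 hours for SAE reports, 7 and 15 calendar days for regulatory ADR reports, and 1 business day for urgent safety information to sites. The unblinding step has none.

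**4. How often the code would matter.** Section 4.3.2 applies to product and placebo alike. Further application stops after the specified allergic reactions, and may be stopped after infection, in either arm. "Patients with allergic reaction or infection may receive appropriate treatments at the" principal investigator's discretion. Product is given only at the site at Visits 2 to 4 (Sections 5.5 and 5.6), so it can be withheld without the code. Section 8.3.3 likewise stops product on pregnancy in both arms. None of these actions depends on the arm. What remains is a residual emergency that the documents do not describe but that Section 4.2 itself provides for.

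**5. What an extra opening costs.**
- The primary endpoint is assessed by the investigator (Section 2.2.1). One opening unblinds that assessor for 1 of about 15 evaluable patients in an arm, 1/15 = 6.7%, or 1/30 = 3.3% of the evaluable total.
- Allocation is by permuted blocks stratified by site, in a 1:1 ratio. The block size is not given, so call it b. If the investigator knows one assignment and the block limits, each other patient in that block has the opposite assignment with probability (b/2)/(b − 1). At the smallest possible block, b = 2, this is 1/1 = 1. At an assumed b = 4 it is 2/3. It falls towards 1/2 as b grows.

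**The case against.** The strongest case for the present wording is that prior sponsor review protects the blind where it matters most. The primary assessor holds the envelopes, the trial is small, and one opening may help predict other assignments at the site. In addition, the stopping rules work without the code, and the one explicit unblinding request outside Section 4.2, an SAE of inconclusive cause, is a causality question that can wait. All of this stands. It is why prior authorisation should stay for non-emergency requests and why the cost of the change must be stated.

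A reader might infer more than the documents support:
- *That the two parts of Section 4.2 contradict each other.* They do not. One says when the code may be revealed and the other says how. If the sponsor answers promptly, both are met. The defect is the missing emergency exception.
- *That the sponsor may refuse, or controls who is unblinded.* The text makes opening conditional on authorisation but never speaks of refusal.
- *That the delay is unlimited and the sponsor cannot be reached.* Contact pages are not in the public text, and Section 4.2 says that centres will be instructed on breaking the blind at initiation. Contacts and response times may be given there. Such instructions would shorten the delay but would not remove the written authorisation step.
- *That the allergic-reaction and infection rules need the code.* Section 4.3.2 contains no step that depends on the arm.
- *That the harm is known to be severe.* The documents give no rate and no scenario from which severity could be judged.

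**Conclusion.** The point holds in a limited form. Section 4.2 reserves the investigator-held key for safety and for decisions that depend on the assignment, yet makes every opening wait for sponsor discussion and authorisation. This is a stated rule that can delay a safety unblinding, and more than an omitted detail.

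Its size cannot be expressed as a number. Cases should be few, because most foreseeable events under Section 4.3.2 can be managed blind. The length of any delay is unknown, because no response time is stated. No alpha, power, sample size or estimate changes.

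The conclusion assumes that investigators follow Section 4.2 as written and that no unseen site instruction overrides it. If such an instruction exists, the protocol text should be brought into line with it.

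**What to change.** Amend Section 4.2 to separate two routes.

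- **Medical emergency in which the decision depends on the assignment:** the investigator may open that subject's envelope at once, signs and dates it, documents the reason in the source document, and sends the request form to the sponsor afterwards, for example within the 24 hours already used for SAE reports. The sponsor representative's signature is then added to the form after the event.
- **All other requests, including SAE causality under Section 4.3.1:** prior discussion with, and authorisation from, the sponsor, as now.

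Adjust the cross-reference in Section 4.3.1 and the Protocol Summary so that it points to the second route. Keep the existing rule that the CRF records the unblinding but not the assignment.

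The drafting cost is one paragraph. The real cost is an occasional extra unblinding of the primary assessor for one patient, with some risk of revealing other assignments in that site's block. Because each opening is documented, the study report can identify the patients affected. The change sets no dose and no clinical rule.

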4.3 Stopping rules and unscheduled visits

4.3.1 Stop the study

The study will be stopped when > 1/3 of patients in the phase I have developed study drug related grade 2 or above SAEs defined as in Section 8. The investigator will determine if SAEs are study drug related without breaking the blind. If the cause of SAE is inconclusive, the investigator can request to break the blind following the procedure stated in Section 4.2.

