All subjects are scheduled to attend a follow-up visit at Day 28 to evaluate the status of the target wound and then enter a 360-day follow-up phase. If the complete wound closure occurs by Day 14, the re-confirmation of wound closure should be performed on Day 28 follow-up. In the case that complete wound closure occurs at some point between Day 14 and Day 28, an additional follow-up visit will be scheduled on Day 42 for the re-confirmation before subject enters the 360-day follow-up phase. If the complete wound closure is not observed on Day 28, patients will have other appropriate treatment at the investigator's discretion. The DSWs will be followed till 100% re-epithelialization.

During the 360 days of follow-up, four follow-up visits will be scheduled on 90 ± 14 days, 180 ± 14 days, 270 ± 14 days and 360 ± 14 days following the subject's Day 28 visit (if no Day 42 visit) or Day 42 visit. In total, 5~6 follow-up visits will be scheduled in this study for all randomized subjects.

The study will be stopped when $> 1/3$ of patients in the phase I have developed study drug related grade 2 or above SAEs defined as in Section 8. The investigator will determine if SAEs are study drug

related without breaking the blind. If the cause of SAE is inconclusive, the investigator can request to break the blind following the procedure stated in Section 4.2.

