Study Product, Dose, Route, Regimen	TWB-103, allogeneic human fibroblasts + gelatin-based hydrogel, applied 2 to 3 times till 100% re-epithelialization or up to 10 days (around once every 3 days); a matching placebo, freezing solution with gelatin-based hydrogel, is used as the control and applied to patients in the same duration and dosing frequency as TWB-103.
Duration of Treatment	During the planned treatment period (14 days), each patient will receive TWB-103+Tegaderm™ or placebo+Tegaderm™ for up to 10 days or to the day of 100% re-epithelialization, whichever comes first, followed by Tegaderm™ alone application from Day 10 to Day 14 if failing to achieve 100% re-epithelialization by Day 10.
Study Visits	
Patients will be scheduled to attend the following visits:
 
1. Screening (within 2 weeks prior to DSW creation)2. Day 0 (treatment begins)3. Day 3 (\pm 1 day)4. Day 7 (\pm 1 day)5. Day 10 (\pm 1 day)6. Day 14 (\pm 2 days, end of treatment)7. Day 28 (\pm 3 days, Follow-up)8. Day 42 (\pm 3 days, Follow-up)

9. 90 ± 14 days after Visit 7 or Visit 8 (Follow-up)

10. 180 ± 14 days after Visit 7 or Visit 8 (Follow-up)

11. 270 ± 14 days after Visit 7 or Visit 8 (Follow-up)

12. 360 ± 14 days after Visit 7 or Visit 8 (Follow-up)

Note: (1) For patients with complete wound closure by Day 14, the confirmation of wound closure will be assessed on Day 28.

(2) Day 42 follow-up is only scheduled when the wound closure is not completed by Day 14 but is observed on Day 28. The wound closure will be re-confirmed on Day 42.

(3) If no Visit 8, Visit 9~12 should be scheduled following Visit 7.

(4) In case patients achieve 100% re-epithelialization before or at Day 10, patients will finish up the assessments on the day with 100% re-epithelialization. This day of 100% re-epithelialization will be the end of treatment and the remaining scheduled treatment visits, if applicable, will be dismissed.

Patient Assignment Patients who meet all eligibility requirements for entry into the study will be randomized into one of the treatment group or control group in 1:1 ratio as shown below:

Treatment Group:

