In Phase I proportion, eligible patients will be recruited sequentially with one week staggering in the initiation of study treatment. Eligible patients will also be randomized into 1:1 ratio into one of Treatment (TWB-103+Tegaderm™) and Control (placebo+Tegaderm™) groups. Phase I plan to recruit 3 evaluable TWB-103+Tegaderm™ treated and 3 evaluable placebo+Tegaderm™ treated patients. Patients in phase I are considered as evaluable when (1) he/she receives at least one dose and has follow-up evaluation at least 14 days after first dose or (2) he/she receives at least one dose and has early withdrawn due to safety reasons before Day 28. When all of those 6 evaluable patients complete the planned treatment period (14 days or till first 100% re-epithelialization, which comes first), the recruitment of patients will be temporarily stopped for 14 days for safety observation. The safety data of TWB-103 before and on Day 28 Visit will be reviewed by the sponsor and the principal investigator. If no safety issue of TWB-103 is decided, the study will enter Phase II portion and eligible patients will be randomized into 1:1 ratio into one of Treatment and Control groups.

Each patient will have treatment for up to 14 days or to the day of 100% re-epithelialization, whichever comes first. Patients assigned to the Treatment Group will receive TWB-103 add-on Tegaderm™ till 100% re-epithelialization or up to 10 days,

whichever comes first and will receive Tegaderm™ alone from Day 10 to Day 14 if re-epithelialization can not be attained by Day 10. Patients assigned to the Control Group will receive placebo+Tegaderm™ till 100% re-epithelialization or up to 10 days, whichever comes first and will receive Tegaderm™ alone from Day 10 to Day 14 if re-epithelialization can not be attained by Day 10. Patients from either group (treatment or control) will have application of Tegaderm™ alone up to Day 28 if 100% re-epithelialization of DSWs is not observed on Day 14 (end of treatment).

Patients will be required to attend scheduled visits at Screening, Day 0 (treatment start day), Day 3, Day 7, Day 10, Day 14 (end of treatment). In case patients achieve 100% re-epithelialization before or at Day 10, patients will finish up the assessments on the day with 100% re-epithelialization. This day of 100% re-epithelialization will be the end of treatment and the remaining scheduled treatment visits, if applicable, will be dismissed.

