If patient develops grade 2 or above SAEs and should exit the study prematurely before Day 14, he/she should be excluded from the primary efficacy analysis, because early censor will result in under estimation of the healing time while treatment group (TWB-103+TegadermTM) is prone to have higher risk of developing treatment related SAE.

In the cases of TWB-103/placebo discontinuation due to allergic reaction or infection, wound assessments performed after onset of allergic reaction or infection will be excluded from statistical analysis.

Healing rates (complete wound closure) of patients at Days 7, 10 and 14 after DSW creation will be analyzed by CMH test. Healing percentage of wounds (ratio of healing and original areas) at Days 7, 10 and 14 after DSW creation will be analyzed by Analysis of variance (ANOVA) model with treatment group and country as factor. Score on short-form McGill pain questionnaire will be analyzed by using Analysis of covariance (ANCOVA) model with treatment group and country as factor and baseline characteristics as covariate. Vancouver Scar Scale will be analyzed by Wilcoxon ranked sum test. The score in each category (pigmentation, vascularity, pliability and height) and the sum score of all category in Vancouver Scar Scale will be analyzed.

All treatment group comparisons will be conducted with significance level of 0.05, using 2-tailed tests.

Demographics and baseline characteristics will be summarized for each group/country by using descriptive statistics.

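### The Phase I stopping rule counts TWB-103 and placebo patients together and leaves its denominator unstated; with all six counted, related SAEs in two of three TWB-103 recipients do not compel a stop

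*Combined protocol and SAP*

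**What the plan says.** The rule is in section 4.3.1 and is repeated in the Protocol Summary under Study Design: "The study will be stopped when > 1/3 of patients in the phase I have developed study drug related grade 2 or above SAEs". It names no arm, prints no count and does not define its denominator. The investigator judges relatedness blinded and may ask to unblind if the cause is unclear.

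Section 4 sets the size ("Phase I plan to recruit 3 evaluable" patients on TWB-103 and the same number on placebo, six in all) and starts patients one week apart. Recruitment pauses for 14 days after the six finish treatment. Then "The safety data of TWB-103 before and on Day 28 Visit will be reviewed by the sponsor and the principal investigator", and "If no safety issue of TWB-103 is decided, the study will enter Phase II portion". No numerical criterion is given for that decision.

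Other relevant text:
- Section 4.2 allows the blind to be broken for safety, "including conditions listed in Section 4.3.1 and 4.3.2", through the investigator's envelope and with sponsor authorization.
- Section 4.3.2 stops dosing patient by patient.
- Section 8.3.2 requires SAE reports within 24 hours.
- Section 10.2.4 says there is no DSMB.
- Section 10.2.2, explaining an exclusion from the efficacy analysis, says the TWB-103 group "is prone to have higher risk of developing treatment related SAE".

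**The concern.** This is the only numerical safety rule at study level, in a trial that sections 1.2.1 and 1.2.4 describe as first in human. Half of the planned denominator is placebo patients. If harm comes from the cells, placebo patients add to the denominator and not to the numerator, so the pooled fraction is least sensitive when the two arms differ. Section 10.2.2 itself anticipates that difference.

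The unstated denominator is a second weakness. The same two events could require a stop or not, depending on whether the team divides by the planned six or by the patients treated when the second event is reported. At stake is whether two harmed recipients out of three lead to a mandatory stop or to an unstructured judgement by the sponsor and the principal investigator.

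**Working it through.** **Inputs.** Threshold: strictly more than 1/3 of Phase I patients (section 4.3.1). Planned size: 3 TWB-103 and 3 placebo (section 4). The documents give no SAE rate and no operating characteristic for the rule, so there is no plan figure to reproduce and every risk below is an assumption.

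**Step 1: the count implied by the fraction.** The smallest number of affected patients k with k/n > 1/3 is:

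| Denominator n | Smallest k |
|---|---|
| 2 | 1 |
| 3, 4 or 5 | 2 |
| 6, 7 or 8 | 3 |

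At six, 2/6 equals 1/3 and fails the strict inequality, so three affected patients are needed. One or two extra non-evaluable patients do not change this. At five, 2/5 = 40% and the rule is met. Among the three TWB-103 recipients alone, 1/3 fails and 2/3 passes, so the same fraction would give a count of two.

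Reading study drug as TWB-103 only would remove placebo events from the numerator. The denominator would still be all Phase I patients, so two recipients out of six would still not meet the rule.

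**Step 2: which outcomes change.** Let a be the affected TWB-103 patients (0 to 3) and b the affected placebo patients (0 to 3), giving 16 outcomes. With n fixed at six, the rule as written stops if a + b ≥ 3. With an added trigger it stops if a ≥ 2 or a + b ≥ 3. The two differ only at (a, b) = (2, 0), and no stop is lost.

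**Step 3: chance that the automatic rule fires, n fixed at six.** Take a and b as independent binomials with risks p and q. With q = 0, the rule as written fires with probability p³, and with the addition 3p²(1 − p) + p³. At p = 0.30 that is 0.027 against 0.189 + 0.027 = 0.216.

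| Assumed risks | As written | With added trigger |
|---|---|---|
| p = 0.30 / 0.50 / 0.70, q = 0 | 2.7 / 12.5 / 34% | 22 / 50 / 78% |
| p = 0.30 / 0.50 / 0.70, q = 0.10 | 9.1 / 24 / 47% | 23 / 51 / 79% |
| p = q = 0.30 / 0.50 / 0.70 | 26 / 66 / 93% | 32 / 70 / 94% |
| p = q = 0.05 | 0.2% | 0.8% |
| p = q = 0.10 | 1.6% | 3.6% |

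The gain is largest when harm is confined to TWB-103. It is small when both arms share the harm, and few extra stops arise at low equal risk.

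**Step 4: burden of the code check.** A check is needed if a + b ≥ 2. The study ends Phase I without a stop, despite a check, at (1, 1) and (0, 2), with probability 9pq(1 − p)²(1 − q)² + 3q²(1 − q)(1 − p)³. At p = q = 0.05 the check probability is 1 − 0.95⁶ − 6 × 0.05 × 0.95⁵ = 0.033, and the continuing probability is 0.0183 + 0.0061 = 0.024.

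| Assumed risks (TWB-103, placebo) | Check needed | Checked, then continues |
|---|---|---|
| 5%, 5% | 3.3% | 2.4% |
| 10%, 10% | 11.4% | 7.9% |
| 30%, 10% | 34.5% | 11.6% |

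**The case against.** **The review already covers this case.** The review before Phase II is mandatory, looks specifically at TWB-103 safety, and must find no safety issue. Staggered starts, 24-hour reporting and the recruitment pause add protection. This stands. A reader might infer that the plan would carry two harmed recipients out of three into Phase II, or that 2.7% against 22% compares stopping with continuing. The documents support neither: the comparison is of an automatic stop with a judgement. What remains is that the judgement has no criterion and comes only after all six have finished treatment.

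**The denominator may be a running count.** Patients enter one at a time, so this reading is open. On it, two events among five or fewer patients stop the study. The flat claim that two recipients can never trigger the rule is therefore not supported. The gap on this reading is confined to a second event reported once all six are in the denominator.

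**Pooling has a purpose.** It suits a blinded relatedness call, and it can detect harm from the vehicle or the procedure, since "a matching placebo, freezing solution with gelatin-based hydrogel, is used as the control". This also stands, and it argues against replacing the pooled count.

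**High SAE risks are speculative.** The documents support none of the assumed rates, and section 1.2.2 cites more than 15 years of human use of the cell line. The risks of 30% to 70% show how the rule behaves if that expectation is wrong. They are not a forecast.

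**An arm-specific check costs blinding.** It does. Phase I patients also enter the investigator-assessed primary efficacy analysis, so the cost is counted in the fix.

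**Conclusion.** The point holds in a limited form. The denominator is undefined. With all six patients in it, related SAEs of grade 2 or higher in two of three TWB-103 recipients and no placebo patient do not meet the only numerical study-level rule. The added trigger closes exactly that outcome, one of 16 on a fixed denominator of six. In that setting, with no placebo events, it lifts the chance of an automatic stop by 19, 37.5 and 44 percentage points at assumed TWB-103 risks of 0.30, 0.50 and 0.70. These figures assume independent patients and risks the documents do not supply, and they give no weight to the discretionary review. The plan has other real safeguards, so this is a gap that should be closed cheaply. It does not show that Phase I is unsafe as designed.

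**What to change.** 1. **Keep the pooled rule and state its denominator**, in section 4.3.1 and the synopsis. Do not replace the fraction with a flat count of three. If a running count is intended, that would remove stops the rule now makes, such as one TWB-103 and one placebo event among the first five patients. If a running count is chosen, note that a single event among the first two patients (1/2) also meets it, and decide whether that is wanted.
2. **Add a second trigger** in both places: stop the study, and do not open Phase II, if two or more TWB-103 recipients in Phase I have a study-drug-related SAE of grade 2 or higher.
3. **Say how it is checked.** When a second affected patient is reported, a named code holder outside the blinded team looks up the affected patients' assignments and returns only stop or continue. Repeat the check at the Day 28 safety review.

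**Cost.** The change is wording in two places and one named role. The documents describe no such role. Section 4.2 refers to a randomization plan that is not part of these documents, so one may already exist. Sample size, endpoints and analyses do not change. The code check would be needed in 3.3% to 34.5% of cases across the three scenarios in the last table, with the study continuing afterwards in 2.4% to 11.6%. Each such continuation tells the team that at most one affected patient was on TWB-103, though not which one.
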